3.6 Intended Use

The Edwards PASCAL System is intended for the percutaneous reconstruction of an insufficient mitral valve in patients with clinically significant, symptomatic mitral regurgitation and:

- New York Heart Association (NYHA) Functional Class II, III and ambulatory IV heart failure
- The primary regurgitant jet is non-commissural. If a secondary jet exists, it must be considered clinically insignificant

A Clinical Investigator's Brochure (CIB) has been prepared for the Edwards PASCAL System. This brochure provides the prior testing conducted on the system components.

3.7 Prior Clinical Studies

[REDACTED]

[REDACTED]

[REDACTED]

[REDACTED]

[REDACTED]

[REDACTED]

[REDACTED]

3.8 Study Device

3.8.1 Device Description

[REDACTED]

[REDACTED]

[REDACTED]	[REDACTED]
[REDACTED]	[REDACTED]
[REDACTED]	[REDACTED]
[REDACTED]	[REDACTED]
[REDACTED]	[REDACTED]

5

⁵ The images in this section are representative of the original version of the PASCAL System

[REDACTED]

3.8.1.1 Edwards Mitral Valve Repair Implant System

[figure not shown]

Figure 2: Implant System (Implant, Steerable Catheter, Implant Catheter), Guide Sheath, and Stabilizer

- **Implant Device** (Figure 3)

[figure not shown]
[figure not shown]

Figure 3: Implant

- **Steerable Catheter** (Figure 4)

[REDACTED]

- **Implant Catheter** (Figure 4)

[REDACTED]

[REDACTED]

- **Loader**

[REDACTED]

3.8.1.2 Edwards Mitral Valve Repair Guide Sheath

[REDACTED]

[figure not shown]

Figure 5: Guide Sheath

Figure 6: Introducer

Figure 7: Loader

3.8.1.3 Edwards Mitral Valve Repair Stabilizer

[REDACTED]

[REDACTED]

Figure 8: Stabilizer

3.8.1.4 Edwards Mitral Valve Repair Table

[figure not shown]

Figure 9: Table

4 DEVICE ACCOUNTABILITY

4.1 Device Shipments

Devices will be transported to the study center when the Clinical Study Agreement is in place, the study center has obtained applicable regulatory (e.g., Ethics Committee, Ministry of Health) approvals, and a patient eligible for implant has been identified.

Devices will be provided to the study center as needed for scheduled implant procedures. All investigational devices used in this study for investigational purposes will be labeled as such per regional requirements.

4.2 Device Accountability Records

All device shipments will have inventory and shipment records will be maintained by both the Study Sponsor and the study center. Devices may be hand carried to participating study centers by the Study Sponsor personnel and will be accompanied by delivery of investigational device documentation (packing lists, transfer of investigational product form, etc.). The Investigator (s) or designee will take inventory of the product and complete the delivery documentation with receipt date, condition of the device and signature. The Investigator will maintain a Device Accountability Log (as provided by the Sponsor) of all investigational devices documenting their receipt, disposition and return during this clinical study. The log will be kept with the documents for the clinical study and will be available for review during Study Sponsor monitoring visits. Upon Sponsor request or when enrollment has ended, Edwards PASCAL System components must be returned to Edwards Lifesciences and the date of return must be recorded on the log.

4.3 Device Storage

The device inventory will be stored in a locked, controlled, cool and dry area as described in the Instructions for Use (IFU) and/or presented on the device labeling. This secured area will be only accessible to the Investigators or approved designee. Only Investigators trained and identified in the Investigator's Agreement and the Delegation of Authority form may use the investigational devices.

4.4 Device Return

The Investigator will be notified in writing upon termination of the clinical study. All unused devices in original package and/or those in opened packages as well as those removed from the original package will be returned to Edwards Lifesciences upon receipt of this notice. The Investigator will receive instructions from the Study Sponsor on the return process. The Investigator's copy of the Device Accountability log must document any unused devices that have been returned.

Used devices may be handled and disposed of in the same manner as hospital waste and bio-hazardous materials in accordance with local regulations. There are no special risks related to the disposal of these devices. All returns and dispositions of devices will be captured on the Device Accountability Log Procedure needed.

4.5 Patient Implant Card

The patient implant card will be supplied with the device.

5 TRAINING

5.1 Investigator Device Training

[REDACTED]

[REDACTED]

5.2 Training of Investigational Center Personnel

[REDACTED]

5.3 Training Documentation

[REDACTED]

[REDACTED]

6 RISKS AND BENEFITS OF THE INVESTIGATIONAL DEVICE AND CLINICAL INVESTIGATION

A risk analysis has been conducted, in accordance with ISO 14971: "Application of risk management to medical devices". The risks associated with this investigational device have been identified by performing Failure Mode and Effect Analysis (FMEA)/Risk Analysis. Risks have been proven minimized through appropriate design control, confirmed by bench testing, pre-clinical animal testing and clinical surveillance presented in the CIB.

During the conduct of the clinical study, the existing risk control measures shall be reviewed to identify if other hazards have been introduced. If any new hazards were introduced by any risk control measures, the associated risk(s) shall be re-assessed and addressed.

6.1 Potential Risks

Complications associated with standard cardiac catheterization, the use of anesthesia and use of the PASCAL system could lead to reoperation, explant, permanent disability, or death.

The following anticipated adverse events have been identified as possible complications of the PASCAL system and/or implant procedure:

- Abnormal lab values;
- access site AV fistula or pseudoaneurysm;
- allergic reaction to anesthetic, contrast, heparin, Nitinol;
- anemia, may require transfusion
- angina or chest pain
- arrhythmias;
- atrial fibrillation;
- atrial septal defect requiring intervention;
- arterio-venous fistula;
- bleeding;
- cardiac arrest;
- cardiac failure/low cardiac output;
- cardiac injury including perforation, obstruction, or dissection that may require intervention;
- cardiogenic shock;

- chordal entanglement or rupture;
- coagulopathy, coagulation defect or disorder, bleeding diathesis;
- conversion to open valve surgery
- conduction system injury which may require permanent pacemaker implantation
- death;
- deterioration of native valve (leaflet tear/tearing, leaflet retraction, leaflet thickening, or other);
- device deterioration (wear, tear, fracture, calcification, or other);
- device migration (including single leaflet device attachment (SLDA), malposition or embolization requiring intervention;
- device thrombosis requiring intervention;
- emergency cardiac surgery;
- deep venous thrombosis;
- reaction to anti-platelet, anticoagulation agents or contrast media
- dyspnea;
- edema
- electrolyte imbalance;
- emboli/embolization including air, particulate, calcific material, or thrombus;
- endocarditis;
- esophageal irritation;
- esophageal perforation or stenosis;
- exercise intolerance or weakness;
- fever;
- failure to deliver PASCAL to the intended site;
- failure to retrieve any PASCAL system components;
- gastrointestinal bleeding or infarct;
- heart failure;
- heart murmur;
- hematoma;
- hemodynamic compromise;
- hemolysis;
- hemorrhage requiring transfusion or intervention;
- hypertension

- hypotension;
- Implantation of additional transcatheter mitral repair device
- infection;
- Inflammation
- Leaflet damage;
- mesenteric ischemia
- mitral valve stenosis
- mitral valve injury;
- multi-system organ failure;
- myocardial infarction;
- nausea or vomiting;
- nerve injury
- neurological symptoms, including dyskinesia, without diagnosis of TIA or stroke
- non-emergent reoperation;
- nonstructural implant dysfunction;
- obstruction of valvular structures, e.g. LVOT obstruction;
- pain or changes at the access site;
- papillary muscle damage;
- paralysis;
- PASCAL system component(s) embolization
- pericardial effusion, cardiac tamponade;
- peripheral ischemia;
- permanent disability;
- pleural effusion;
- prolonged ventilation;
- pulmonary edema;
- pulmonary embolism;
- renal failure;
- renal insufficiency;
- respiratory compromise, respiratory failure, atelectasis, pneumonia
- reoperation;
- restenosis;

- retroperitoneal bleed;
- septicemia, sepsis
- shock, e.g. anaphylactic or cardiogenic
- skin burn, injury or tissue changes due to exposure to ionizing radiation
- syncope;
- systemic peripheral ischemia;
- thromboembolic events, stroke, transient ischemic attack, clusters, or other neurological changes;
- thromboembolism (permanent or transient pulmonary and/or neurological events)
- transvalvular flow disturbances;
- urinary tract infection and/or bleeding
- vascular injury or trauma, dissection or occlusion, that may require intervention
- valvular regurgitation;
- vessel spasm
- ventricular wall, atrial wall or septal damage, abrasion, or perforation;
- wound dehiscence, delayed or incomplete healing;
- worsening of heart failure;
- worsening mitral regurgitation / valvular insufficiency

There may be other risks that are unknown at this time. All safety events will be collected and reviewed periodically throughout the entire study periodically. The Investigators will be notified of any additional risks identified that could affect the health, safety or welfare of the study patients.

6.2 Risk Management

All efforts will be made to minimize the identified risks. Careful patient selection will be performed by the Heart Team¹¹ in collaboration with the Sponsor.

The Investigators selected at each site will include an Interventional Cardiologist or Surgeon who is an expert in mitral valve disease and experienced in performing transcatheter mitral valve repair and/or replacement, and skilled in percutaneous coronary interventions and structural heart interventions to assess patient risk and anatomical suitability. Each implanting physician will be thoroughly trained on the investigational device before first implantation in a patient. There will be strong collaboration between interventional cardiology or cardiac surgery and a designated team of nurses, technicians and colleagues from supporting medical disciplines (e.g., anesthesiologist, echocardiographer, and radiologist).

The procedure will be performed in an operating room, catheterization lab or hybrid operating room with fluoroscopic and echocardiographic imaging capabilities.

All adverse events will be thoroughly monitored and reviewed by the Study Sponsor and DSMB. Stopping rules will be applied for patient safety throughout enrollment.

6.3 Benefits

[REDACTED]

7 CLINICAL INVESTIGATION

7.1 Study Design

This is a multi-center (up to 20 sites initially), multi-national, prospective, single arm study. The analysis population will consist of 60 patients. No site will be allowed to enroll more than 20% of the analysis population in the primary cohort. All enrolled study patients will be assessed for clinical follow-up at the following intervals: 30 days, 6 months, 1 year and annually for 5 years post implant procedure. In addition, the study allows for 0 to 3 roll-in patients per site where allowed, for a total maximum of 60 roll-in patients. The overall study therefore allows for up to 120 patients: 60 in the analysis population, and up to 60 additional roll-in patients.

Following completion of the primary cohort of 60 patients in the analysis population (up to 45 of which may be US patients), an additional 50 patients will be enrolled in the U.S. at up to 15 clinical sites.

7.2 Study Objectives

The objectives of this clinical study are to:

- Evaluate the safety and performance of the Edwards PASCAL System
- Provide guidance for future clinical study designs utilizing the Edwards PASCAL System
- Provide guidance for future Edwards PASCAL System development efforts

7.3 Study Population

Adult patients with clinically significant, symptomatic, mitral regurgitation despite optimal medical therapy and/or are being considered by the heart team for standard mitral valve repair or replacement.

7.4 Study Duration

[REDACTED]

[REDACTED]

[REDACTED]

[REDACTED]

[REDACTED]

[REDACTED]

7.5 Primary Endpoints

Safety:

Composite of major adverse events (MAE) defined as cardiovascular mortality, stroke, myocardial infarction, new need for renal replacement therapy, severe bleeding and re-intervention for study device related complications at 30 days.

Performance:

- Device success: device is deployed as intended and the delivery system is successfully retrieved as intended at the time of the patient's exit from the cardiac catheterization laboratory. Per device analysis.
- Procedural success: device success with evidence of MR reduction \leq MR2+ at discharge and without the need for a surgical or percutaneous intervention prior to hospital discharge. Per patient analysis.
- Clinical success: procedural success with evidence of MR reduction \leq MR2+ and without MAEs at 30 days. Per patient analysis.

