1 OVERVIEWS

1.1 Study Assessment Overview

Table 1: Study Assessments

Study Assessments	Screening/Baseline	Implant Procedure ¹ (Day 0)	Post Implant (within 12-24 hrs)	Discharge or 7 days Post- Procedure ²	1 Month (30 ± 7 days)	6 Month (180 ± 30 days)	1 Year (± 45 days)	Annual 2-5 Year (± 45 days)
Informed Consent	X							
Review of inclusion/exclusion criteria	X							
Medical History	X							
Logistic EuroSCORE-I, EuroSCORE-II, STS score	X							
Clinical Evaluation	X		X	X	X	X	X	X
NYHA Class Assessment	X				X	X	X	X
NIH Stroke Scale/Modified Rankin Scale ³	X			X	X	X	X	X
Health Status Questionnaires	X				X	X	X	
Six Minute Walk Test	X				X	X	X	
Safety Evaluation		X	X	X	X	X	X	X
CBC and Platelet count	X		X	X	X	X	X	X
Complete Metabolic Panel	X				X	X	X	X
BNP/NT-pro-BNP	X			X	X	X	X	X
βHCG ⁴	X							
Serum creatinine	X		X	X	X	X	X	X
Coagulation profile (PT or INR, PTT)	X		X	X				
Troponins and CK-MB	X		X	X				
ECG	X	X	X	X	X	X	X	X
Transesophageal Echocardiogram	X	X						
Transthoracic Echocardiogram	X			X	X	X	X	X
Procedural Angiography		X						
Invasive Hemodynamic Monitoring		X						
Magnetic Resonance Imaging (optional, as deemed appropriate by Investigator)	X				X	X	X	X

¹ Implant procedure must be scheduled within 60 days of baseline TTE and 90 days of baseline TEE

[figure not shown]
² Discharge or 7 days post-procedure, whichever comes first

³ Modified Rankin Scale (mRS) will be conducted at baseline for all patients with a history of stroke, and at each follow-up visit for all patients who experience a stroke at any time period during the trial. The assessment should also be completed closest to 90 days post event.

⁴ βHCG for women who are not sterile or post-menopausal

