7.8.7.7 Discharge

The following study procedures will be performed at discharge or at 7 days of procedure, whichever comes first.

- Clinical Evaluation and Concomitant Medication
- Safety Evaluation
- NIH Stroke Scale
- Clinical Laboratory Tests
- Standard 12-lead ECG
- Comprehensive TTE

Discharge data to be collected will be detailed in the CRF; the data include but is not limited to the information listed in the following table.

Table 6: Discharge Information

General Information	Clinical Information	Laboratory Measurements

 • Discharge date 	
 • Clinical evaluation (vital signs, height, weight) • Concomitant medication (incl. antiplatelet/anticoagulant therapy) • Safety evaluation • NIH Stroke Scale/Modified Rankin Scale* • TTE measurements • 12 lead ECG results 	
 • CK • Troponin, if applicable • CK-MB, if applicable • BNP or NT-pro-BNP • CBC and platelets • Serum creatinine • PTT or PT/INR

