10.2 Core Laboratory

An echocardiography core laboratory will be used for the independent assessment of image findings. Standard measurement processes will be designed by the independent core laboratory and specified in written core laboratory guidelines. Each of the selected investigative sites will receive training on the acquisition, interpretation (in especially regarding patient selection) and transmission of images. Any additional (unscheduled) imaging data should be documented and sent to Edwards.

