	
Ordinary physical activity results in fatigue, palpitation, dyspnea, or anginal pain.
 
Class III: Patients with cardiac disease resulting in marked limitation of physical activity. They are comfortable at rest. Less than ordinary physical activity causes fatigue, palpitation dyspnea, or anginal pain.
 
Class IV: Patients with cardiac disease resulting in inability to carry on any physical activity without discomfort. Symptoms of cardiac insufficiency or of the anginal syndrome may be present even at rest. If any physical activity is undertaken, discomfort is increased.

Nonstructural Dysfunction	Abnormality extrinsic to the repair device that results in valve dysfunction (stenosis, regurgitation or both)
Patient	A person with the disease (mitral regurgitation) being screened to participate in the clinical study.
Pre-existing condition	A pre-existing condition is one that is present prior to enrollment in the trial
Procedural Success	Device success with evidence of MR reduction \leq MR2+ at discharge and without the need for a surgical or percutaneous intervention prior to hospital discharge. Per patient analysis.
Rehospitalization (M-VARC 2015 Definition and Sponsor)	
Rehospitalization
 
For the purpose of this trial, rehospitalization is defined as any unplanned admission to the hospital (including an emergency department visit) for either a diagnostic or therapeutic purpose following discharge from the index hospitalization. ER (Emergency Room) visits will be explicitly presented separately from the inpatient hospitalizations.
 
Rehospitalizations will be classified as either:
 
 ○ Admission to an inpatient unit (treated by a physician in a hospital for at least a 24 hour period) OR ○ Visit to an ER unit (typically less than 24 hours) AND diagnostic procedure and/or therapeutic intervention 
Additionally, duration of admission will be indicated as lasting:
 
 ○ < 24 hours OR ○ \geq 24 hours 
All rehospitalizations will be classified to determine whether the hospitalization was related to:

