### 5.2. Visit Windows

The follow-up schedule and analysis windows are listed below.

- Post implant (within 24 hrs)
- Discharge visit (discharge or 7 days post-procedure, whichever comes first)
- 30-Day Visit  $\pm$  7 Days [23, 37 days]
- 6-Month Follow-up (180  $\pm$  30 days) [150, 210 days]
- 12-Month Follow-up (365  $\pm$  45 days) [320, 410 days]
- 2 years (730 days)  $\pm$  45 days [685, 775 days]
- 3 years (1095 days)  $\pm$  45 days [1050, 1140 days]

- 4 years (1460 days)  $\pm$  45 days [1415, 1505 days]
- 5 years (1825 days)  $\pm$  45 days [1780, 1870 days]

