#### 6.6. Additional Analyses per FDA

Per FDA, the success rates based the following definitions will be summarized by counts and percentages.

FDA Device Success (30 day and all post-procedural intervals):

- Alive and stroke free, with
- Original intended device in place, and
- No additional surgical or interventional procedures related to access or the device since completion of the original procedure (i.e., exit from the cath lab/OR), and
- Intended performance of the device:
- Structural performance: No migration, embolization, detachment, fracture, hemolysis, thrombosis or endocarditis, etc., and
- Hemodynamic performance: Maintenance of relief of insufficiency without producing stenosis (stenosis = MV gradient > 5 mmHg; insufficiency = MR >2+), and
- Absence of para-device complications (e.g., leaflet, chordae or papillary muscle damage; LVOT gradient increase > 10 mmHg; hemodynamically significant ASD requiring closure)

FDA Procedural Success (30 day):

- Device success, and
- No device or procedure related SAE's (life threatening bleed; major vascular or cardiac structural complications requiring unplanned reintervention or surgery; stage 2 or 3 AKI (includes new dialysis); MI or need for PCI/CABG; severe HF or hypotension requiring IV inotrope, ultrafiltration or MCS; prolonged intubation > 48 hours)

FDA Technical Success (at exit from OR):

- Alive, with
- Successful access, delivery and retrieval of the device delivery system, and
- Deployment and correct positioning (including repositioning /recapture if needed) of the single intended device, and
- No need for additional unplanned or emergency surgery or re-intervention related to the device or access procedure

FDA Individual Patient Success (1 year):

FDA Device success and all of the following:

- No re-hospitalizations or re-interventions for the underlying condition (e.g., MR, HF)
- Return to prior living arrangement (or equivalent)
- Improvement vs. baseline in symptoms (e.g., NYHA Class improvement > 1 class)
- Improvement vs. baseline in functional status (e.g., 6MWT improvement > 25 meters)
- Improvement vs. baseline in QoL (e.g., KCCQ improvement > 10)

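### Procedural success does not require survival to discharge: an in-hospital death after the day-7 echo can count as a success, and one before the echo leaves the denominator

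*Protocol*

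**What the plan says.** Protocol 7.5 builds procedural success from three parts: device success, MR of 2+ or less, and freedom from re-treatment. The last two are worded "at discharge and without the need for a surgical or percutaneous intervention prior to hospital discharge". Protocol Section 17 and SAP 3.1 repeat the definition. Device success is judged "at the time of the patient's exit from the cardiac catheterization laboratory. Per device analysis", so it says nothing about what happens later in the stay.

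The echo behind the MR part is scheduled in Protocol 7.8.7.7: "The following study procedures will be performed at discharge or at 7 days of procedure, whichever comes first". Footnote 2 to Protocol Table 1 gives the same rule. SAP 5.2 uses it as the analysis window: "Discharge visit (discharge or 7 days post-procedure, whichever comes first". The next scheduled TTE is at the 30-day visit (days 23 to 37).

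SAP 6.1b bases percentages on subjects with evaluable data, unless otherwise specified, and removes those with missing data from the denominator. SAP 6.3 summarises procedural success by counts and percentages and gives no rule for death.

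SAP 6.6 does require survival in the additional FDA definitions. FDA Technical Success requires the patient to be alive, and FDA Device Success begins "Alive and stroke free, with".

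**The concern.** For a stay of more than 7 days, two parts of the same endpoint run on different clocks. MR is read at day 7, while re-treatment is counted up to the day the patient leaves hospital. Survival is on neither clock. A death between the day-7 TTE and discharge therefore breaches no written condition, although few readers would call that procedure successful.

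A death before the TTE goes wrong in another way. There is no MR grade, so the patient is not a success, but the general missing-data rule removes the patient instead of counting a failure.

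Both effects push the rate upwards. The same patient could be a procedural success under the protocol and a failure under the FDA definition in the same report, with death as the only reason.

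**Working it through.** The plan gives no target rate, margin or power for procedural success (Protocol 9.1 justifies the size by precedent), so there is no figure to reproduce. The check is a reading of the text, followed by the size of one misclassified patient.

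**Cases.** In each, assume device success and no in-hospital intervention.

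| Course | Result under the current text |
|---|---|
| Discharged alive by day 7, TTE at discharge 2+ or less | Success, read at true discharge |
| In hospital past day 7, day-7 TTE 2+ or less, discharged alive | Success, with MR read at day 7 |
| In hospital past day 7, day-7 TTE 2+ or less, dies before discharge | No component fails: success |
| Dies in hospital before the discharge/day-7 TTE | No MR evidence: not a success; out of the denominator under SAP 6.1b |

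The third and fourth rows are the problem.

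**Inputs.** n = 60 (analysis population, Protocol 7.1); n = 30 (first analysis, Protocol 9.3); n = 60 + 50 = 110 (pooled cohorts, Protocol 7.1 and 9.3). Observed success counts of 57/60 and 28/30 are assumptions for illustration. Intervals are exact Clopper-Pearson 95%, as in SAP 6.1b.

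**Death after a qualifying day-7 TTE, counted as success instead of failure.** The overstatement is k/n for k patients.
- n = 60: 1/60 = 1.67 points; n = 30: 1/30 = 3.33 points; n = 110: 1/110 = 0.91 points.
- If 57/60 = 95.0% [86.1, 99.0] includes one such patient, the corrected figure is 56/60 = 93.3% [83.8, 98.2]. With two it is 55/60 = 91.7% [81.6, 97.2].
- If 28/30 = 93.3% [77.9, 99.2] includes one, the corrected figure is 27/30 = 90.0% [73.5, 97.9].

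**Death before the TTE, excluded instead of failed.** The overstatement is s/(n − k) − s/n for s successes.
- n = 60, s = 57, k = 1: 57/59 = 96.6% [88.3, 99.6] against 57/60 = 95.0% [86.1, 99.0], a difference of 1.6 points.
- n = 30, s = 28, k = 1: 28/29 = 96.6% against 28/30 = 93.3%, a difference of 3.2 points.

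**How often.** The documents give no length of stay and no in-hospital death rate. As an assumed range, if a proportion p of patients is affected, the chance of at least one among 60 is 1 − (1 − p)^60. This is 45% at p = 1% (0.6 patients expected) and 95% at p = 5% (3.0 expected).

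**The case against.** The strongest reply is that the text does not fix the reading assumed here. The endpoint refers to discharge, not to the discharge visit. Taken literally, a patient who never leaves hospital alive has no result at discharge and cannot be a success. The table shells, which are a separate part of the SAP (SAP 10), may settle the derivation. This stands as a caution, but SAP 5.2 gives the term a day-7 cap and nothing in the two documents says otherwise. The ambiguity is itself a reason to write the rule down.

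Three stronger readings are tempting, and the documents do not support them.
- *Every in-hospital death counts as a success.* A death before the TTE leaves no evidence of MR reduction and so is not a success. The fault there is the lost denominator.
- *A return of severe MR after day 7 without re-treatment is plainly a success.* The clause refers to the need for an intervention, not to having one, so such a patient may not satisfy it. The text leaves this open.
- *The error passes into clinical success.* That endpoint has its own conditions at 30 days: MR of 2+ or less and no MAE. Section 17 classes any death not clearly non-cardiovascular as cardiovascular, so most such deaths fail clinical success. Only a clearly non-cardiovascular death is left without a defined status.

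It is also fair to say that no death would be hidden. All-cause mortality at 30 days (SAP 6.4), 30-day MAE and the FDA definitions are all reported. There is no performance goal, so no decision rule changes. This limits the weight of the point, but it does not correct the procedural success figure. Finally, one might suppose that longer stays are the complicated cases. That is plausible, but the documents do not show it, and the conclusion does not need it.

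**Conclusion.** The point holds in a limited form. None of the three definitions requires survival. On the most natural reading with SAP 5.2, a death in hospital after a qualifying day-7 TTE counts as a success, and a death before that TTE drops out under SAP 6.1b. Both raise the reported rate: about 1.7 points per patient at n=60 and 3.3 at n=30 for the first kind, and slightly less for the second at the assumed success counts. The per-patient figures take the full 60 or 30 as the denominator; a smaller per-protocol set would make each patient count for slightly more. How many patients are affected is unknown and may be none. Because the analysis is descriptive and the deaths appear in other endpoints, this is a worthwhile correction to a primary performance endpoint, not a threat to the study's conclusions.

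**What to change.** - In Protocol 7.5, Protocol Section 17 and SAP 3.1, add to procedural success the condition that the patient is alive at hospital discharge.
- In SAP 6.3, state that any in-hospital death is a procedural failure and stays in the denominator, whether or not an echo was obtained. SAP 6.1b allows such an exception.
- In the same places, state that the MR component is read from the scheduled discharge/day-7 TTE.
- Optionally, add a sensitivity analysis that uses a later in-hospital TTE where the core laboratory has read one. This should not be the main rule. Such scans are not scheduled, so the MR grade would come from different times in different patients. Protocol 10.2 says only "Any additional (unscheduled) imaging data should be documented and sent to Edwards", not that the core laboratory reads them. The core-laboratory reading would have to be arranged.

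The main change costs a short amendment to three definitions and one scoring rule. It needs no new visit or scan: the discharge date (Protocol Table 6) and length of stay (SAP 7.5) are already collected. The downside is that the reported success rate may be slightly less favourable.
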